- 12. Subject has a history of neurological abnormalities including abnormal EEG at screening or brain injury including traumatic injury, perinatal cerebropathy and postnatal brain damage, blood-brain barrier abnormality, and angioma cavernous.
- 13. Subject has a history of cerebral arteriosclerosis.
- 14. Subject has a condition that can potentially reduce drug clearance (eg, renal or hepatic insufficiency).
- 15. Subject has current or recent (within 6 months) gastrointestinal disease that would be expected to influence the absorption of drugs (ie, a history of malabsorption, any surgical intervention known to impact absorption [eg, bariatric surgery or bowel resection], esophageal reflux, peptic ulcer disease, erosive esophagitis, or frequent [more than once per week] occurrence of heartburn).

- 16. Subject has a history of cancer, except basal cell carcinoma which has been in remission for at least 5 years prior to Check-in (Day 1).
- 17. Subject has a positive test result for hepatitis B surface antigen (HBsAg), hepatitis C virus (HCV) antibody, or a known history of human immunodeficiency virus (HIV) infection at Screening.
- 18. Subject has used nicotine-containing products (including but not limited to cigarettes, pipes, cigars, chewing tobacco, nicotine patch, or nicotine gum) within 28 days prior to Check-in Day -1. Cotinine test is positive at Screening or Check-in (Day -1).
- 19. Subject has poor peripheral venous access.
- 20. Subject has donated or lost 450 mL or more of his or her blood volume (including plasmapheresis), or had a transfusion of any blood product within 90 days prior to first dose of study drug.
- 21. Subject has a Screening or Check-in (Day -1) abnormal (clinically significant [CS]) ECG. Entry of any subject with an abnormal (not clinically significant [NCS]) ECG must be approved, and documented by signature of the principal investigator or medically qualified subinvestigator. In the case of a QTcF interval >450 ms or >480 ms (subjects with Bundle Branch Block) or PR outside the range of 120 to 220 ms, assessment may be repeated once for eligibility determination at the Screening Visit and/or Check-in (Day -1) Visit.
- 22. Subject has a supine blood pressure outside the ranges of ≥90 to ≤140 mm Hg for systolic and ≥50 to ≤90 mm Hg for diastolic. If out of range, assessment may be repeated once for eligibility determination at the Screening Visit and/or Check-in (Day -1).

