- 23. Subject has a resting heart rate outside the range of 50 to 90 bpm (not on ECGs). If out of range, the assessment may be repeated once for eligibility determination at the Screening Visit and/or Check-in (Day -1).
- 24. Subject has abnormal Screening or Check-in (Day -1) laboratory values that suggest a clinically significant underlying disease or subject has the following lab abnormalities: ALT and/or AST >1.5 ULN.
- 25. Subject has a risk of suicide per the C-SSRS (a score of 4 or 5 on ideation or any suicidal behavior) or according to the investigator's clinical judgment, has made a suicide attempt in the previous 6 months, or has a history of deliberate self-harm in the past 6 months.

Additional exclusion criteria for collection in SRD/MRD Cohort 3:

- 26. The subject has had collected within 6 months prior to Check-in (Day -1).
- 27. The subject has a known hypersensitivity to the anesthetic or its derivatives used during collection or any medication used to prepare the area of lumbar puncture.
- 28. The subject has any skin condition, abnormality of the lumbar spine, medical or surgical condition that would preclude lumbar puncture (eg, coagulopathy, local or systemic infection,

left ventricular outflow obstruction, aortic stenosis, raised intracranial pressure, previous back surgery).

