5.0 ANALYSIS ENDPOINTS

5.1 **Primary Endpoints**

The primary endpoints will be the following safety variables:

- Percentage of subjects who experience at least 1 treatment-emergent adverse event (TEAE).
- Percentage of subjects who discontinue due to an AE.
- Percentage of subjects who meet the markedly abnormal criteria for safety laboratory tests at least once post-dose.
- Percentage of subjects who meet the markedly abnormal criteria for vital sign measurements at least once post-dose.
- Percentage of subjects who meet the markedly abnormal criteria for safety electrocardiogram (ECG) parameters at least once post-dose.
- Percentage of subjects who experience clinically significant abnormal changes in EEG measurements at least once post-dose.
- Columbia-Suicide Severity Rating Scale (C-SSRS):
 - Treatment-emergent suicidal ideation compared to Baseline, as measured by an increase in suicidal ideation category (1-5 on the C-SSRS) during treatment from the maximum suicidal ideation category at Baseline, or any suicidal ideation during treatment if there was none at Baseline.
 - Treatment-emergent suicidal behavior compared to Baseline, as measured by an increase in suicidal behavior category (6-10 on the C-SSRS) during treatment from the maximum suicidal behavior category at Baseline, or any suicidal behavior during treatment if there was none at Baseline.

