7.9.1 Adverse Events

A TEAE will be defined as an AE or a SAE that occurs or gets worse after receiving the first dose of study drug and within 30 days (onset date – last date of dose + $1 \le 30$) after the last dose of study drug. A TEAE may also be a pretreatment event (PTE) or a concurrent medical condition diagnosed prior to the date of first dose of study drug that increases in severity after the start of dosing. Adverse events data with onset occurring more than 30 days after last dose of study drug (AE start date – last dose date >30) will be listed, but not included in the summary tables.

AE verbatim reported terms will be coded by system organ class (SOC), high-level term (HLT) and preferred term (PT) using MedDRA.

The following is a list of AE summary tables that will be generated:

- Overview of TEAE.
- TEAEs by SOC and PT at subject and event level.
- Subject Mappings for TEAEs.
- TEAEs by PT.
- Non-Serious TEAEs by PT.

- Relationship of TEAEs to Study Drug by SOC and PT.
- Drug-Related TEAEs by SOC and PT.
- Intensity of TEAEs by SOC and PT.
- Intensity of Drug-Related TEAEs by SOC and PT.
- PTEs by SOC and PT
- Serious PTEs by SOC and PT.

A subject with 2 or more different AEs within the same level of the MedDRA term will be counted only once in that level using the most extreme incident for the intensity tables, and relationship to study drug for the causality tables.

Data listings will be provided for all AEs (including PTEs for enrolled subjects), AEs leading to study drug discontinuation, AEs leading to study visit discontinuation, SAEs, and AEs resulting in death.

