7.9.2 Clinical Laboratory Evaluations

Clinical laboratory tests include hematology, serum chemistry and urinalysis.

Descriptive statistics (N, mean, median, SD, minimum and maximum) of clinical laboratory variables in SI units will be summarized for Baseline, postdose, and change from Baseline at each visit. Only the scheduled measurements will be included in the summary. No statistical tests will be performed.

Individual results for hematology and chemistry laboratory tests will be evaluated against the Takeda predefined laboratory markedly abnormal value (MAV) criteria (Appendix A) using the result and criteria in SI units. All subjects with results that meet the MAV criteria will be presented in a data listing. The number and percentage of subjects with at least one postdose markedly abnormal laboratory test result will also be summarized. The mapping of the subjects who meet the MAV criteria after dosing will be listed as a table. All postdose clinical laboratory results within 7 days of the last dose, including scheduled and unscheduled measurements, will be included in the MAV summaries.

All clinical laboratory data will be presented in both SI and conventional units in data listings.

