7.9.3 Vital Signs

Vital signs will include body temperature (oral), supine blood pressure (resting more than 5 minutes), respiration rate, and heart rate. Heart rate and blood pressure will be measured after 5 minutes supine and again at 1 and 3 minutes after standing.

Descriptive statistics (N, mean, median, SD, minimum and maximum) of these vital signs will be summarized for Baseline, postdose, and change from Baseline at each visit. Only the vital signs collected at the scheduled visits or time points will be included in the summary. No statistical tests will be performed for the observed vital signs.

| TAK-653-1001 | Page 26 of 32 |
|---------------------------------|----------------|
| Statistical Analysis Plan Final | 22 August 2017 |

All individual vital signs that meet Takeda's predefined MAV criteria (Appendix B) will be listed. The number and percentage of subjects with at least one postdose markedly abnormal vital sign measurement will be summarized. The mapping of the subjects who meet the MAV criteria after dosing will be listed as a table. All postdose vital signs within 7 days of the last dose, including both scheduled and unscheduled measurements, will be included in the MAV summaries.

7.9.4 12-Lead ECGs

ECG measurements include clinical interpretation, heart rate, and PR, QRS, RR, QT, and QTcF intervals.

Descriptive statistics (N, mean, SD, median, minimum, and maximum) of the quantitative ECG will be summarized for Baseline, postdose, and change from Baseline at each visit. Only the ECGs collected at the scheduled visits or time points will be included in the summary. No statistical tests will be performed for the observed ECGs.

All individual ECGs that meet Takeda's predefined MAV criteria (Appendix C) will be listed. The number and percentage of subjects with at least one postdose markedly abnormal ECG measurement will be summarized. Subjects who meet the MAV criteria after dosing will be mapped to their respective qualifying ECG result. All postdose MAV ECGs within 7 days of the last dose, including both scheduled and unscheduled measurements, will be included in the MAV summaries.

For ECG interpretation data, shift tables will be provided for the number and percentage of subjects who change status on the interpretation from Baseline to each scheduled postbaseline measurement.

All ECG data will be presented in data listings.

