Appendix B Criteria for Markedly Abnormal Values for Vital Signs

| Parameter | Unit | Lower Criteria | Upper Criteria |
|---------------|------|----------------|--|
| Heart Rate | bpm | < 50 | > 120 |
| PR | msec | ≤ 110 | ≥ 220 |
| RR | msec | ≤ 600 | \geq 1440 |
| QRS | msec | ≤ 75 | ≥ 110 |
| QT Interval | msec | \leq 50 | \geq 460 |
| QTcF Interval | msec | ≤ 50 | >=450 or >=30 change from Baseline or >=60 change from Baseline |

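### The ECG markedly-abnormal primary endpoint has no Baseline condition, although entry rules admit subjects who already meet several of its limits

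*SAP*

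**What the plan says.** **Endpoint and counting rule.** SAP 5.1 lists as a primary endpoint: "Percentage of subjects who meet the markedly abnormal criteria for safety electrocardiogram (ECG) parameters at least once post-dose". SAP 7.9.4 turns this into a count: "The number and percentage of subjects with at least one postdose markedly abnormal ECG" result, using scheduled and unscheduled postdose ECGs up to 7 days after the last dose. Vital signs (SAP 7.9.3) and laboratory tests (SAP 7.9.2) follow the same form: "The number and percentage of subjects with at least one postdose markedly abnormal vital sign measurement will be summarized" and "The number and percentage of subjects with at least one postdose markedly abnormal laboratory test result will also be summarized".

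**Other primary endpoints refer to the pre-dose state.** For adverse events, SAP 7.9.1 says: "A TEAE will be defined as an AE or a SAE that occurs or gets worse after receiving the first dose". In SAP 5.1 the C-SSRS endpoints require an increase from Baseline or a new occurrence, and the EEG endpoint is worded in terms of changes.

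**Entry rules (Protocol 7.2).**
- Item 21 excludes clinically significant ECG abnormalities. It lets a subject with an abnormal but not clinically significant ECG enter with signed approval. Its numeric thresholds are a "QTcF interval >450 ms or >480 ms (subjects with Bundle Branch Block) or PR outside the range of 120 to 220 ms", with one repeat allowed.
- Item 23 excludes a subject with a "resting heart rate outside the range of 50 to 90 bpm (not on ECGs").
- No item gives a numeric limit for QRS or uncorrected QT.

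**MAV limits (SAP Appendix C).** The heart rate row reads "Heart Rate | bpm | < 50 | > 120". The other rows used below are PR, QRS, QT and QTcF. The QTcF row combines an absolute limit with change-from-Baseline limits.

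**The concern.** A subject who is over an ECG limit before dosing, and stays there, enters the numerator of a primary safety endpoint without anything having changed on treatment. The parameters where this can happen most readily, heart rate and QT, are ones the trial watches closely. Protocol 6.2.4 names reduced heart rate as a key risk, and Protocol 6.3.1 lists QT prolongation and bradycardia among the cohort stopping criteria. A percentage that mixes pre-existing and new findings, at six active subjects per dose, is hard to read as evidence for or against a dose-related effect.

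**Working it through.** The documents state no MAV rate, so there is no plan figure to reproduce. The check compares limits and then works out what one subject does to a percentage.

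**1. Entry limits against MAV limits** (Protocol 7.2; SAP Appendices A to C)

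| Parameter | Admitted at entry | MAV | Overlap |
|---|---|---|---|
| ECG heart rate, bpm | no ECG limit | below 50, above 120 | yes |
| QRS, ms | no numeric limit | ≤75, ≥110 | yes |
| QT, ms | no numeric limit | ≥460 (high side) | yes, step 2 |
| QTcF with bundle branch block, ms | up to 480 | ≥450 | 450 to 480 |
| QTcF otherwise, ms | up to 450 | ≥450 | 450 only |
| PR, ms | 120 to 220 | ≤110, ≥220 | 220 only |
| Supine pulse, bpm | 50 to 90 | below 40, above 110 | none |
| Supine systolic, mm Hg | 90 to 140 | below 85, above 160 | none |
| Supine diastolic, mm Hg | 50 to 90 | below 45, above 100 | none |
| ALT/AST, × ULN | up to 1.5 | above 3 | none |

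The QTcF and PR rows treat the thresholds in item 21 as entry limits. Its text attaches them to a permitted repeat. If they were only triggers for a repeat, the overlap would be wider.

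**2. QT of 460 ms within the QTcF entry limit.** Fridericia: QTcF = QT / RR^(1/3), with RR = 60/heart rate in seconds.
- At 50 bpm: RR = 1.200, so QT 460 corresponds to QTcF 460/1.200^(1/3) = 432.9 ms.
- At 55 bpm: RR = 1.091, so QTcF = 460/1.091^(1/3) = 446.8 ms.
- At 60 bpm: RR = 1.000, so QTcF = 460 ms, above the 450 ms limit.

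A subject with a slow but admissible heart rate can therefore meet the QT criterion while satisfying the QTcF entry limit.

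**3. Opportunities to be counted** (Protocol Appendices A to C). Part 1 schedules seven ECGs after dosing: four on Day 1, then Days 2, 5 and 7 (or 8). Part 2 schedules six after the first dose: Days 6, 9, 12, 15, 18 and 21. One result over the limit is enough.

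**4. Weight of one subject.** Each dose level has 6 active subjects: 1/6 = 16.7%; two subjects give 2/6 = 33.3%. SAP 7.9 takes SRD Cohort 3 out of the main summaries. SAP 4.4 lists six SRD and five SRD/MRD cohorts, so five cohorts × 2 = 10 placebo subjects are pooled in each part: 1/10 = 10%. Protocol 13.1.5 removes only the fed data. On that reading Part 1 would pool 6 × 2 = 12, and one subject would weigh 1/12 = 8.3%.

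**5. Chance that a group contains such a subject.** The documents give no prevalence *p* of persistent Baseline ECG MAVs, so this is an assumed range. P(at least one of n) = 1 − (1 − p)^n.

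| Assumed p | n = 6 (one dose) | n = 30 (five doses, one part) |
|---|---|---|
| 2% | 11% | 45% |
| 5% | 27% | 79% |
| 10% | 47% | 96% |

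**6. Expected comparison with placebo.** Let q be the rate of new MAVs among the remaining subjects. The reported rate is p + (1 − p)q. If q is zero in both groups, both report p and the expected difference is zero. With p = 10%, q = 10% on active and q = 0 on placebo, the rates are 0.10 + 0.90 × 0.10 = 19% and 10%. The difference is 9 points.

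**The case against.** The strongest reply is that the count is descriptive, follows the protocol's endpoint wording, and applies equally to randomized placebo subjects. No tests are planned on ECG data and the sample size is not power-based. The figure of 16.7 points is the weight of any single event in a group of six, not a bias. SAP 7.9.4 also provides change-from-Baseline summaries, shift tables for ECG interpretation, listings of ECGs meeting the MAV criteria and of all ECG data, and a mapping of affected subjects. The QTcF criterion already has change-from-Baseline limits.

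Much of this stands, and it rules out several stronger readings that a reader might infer:
- **That all three MAV endpoints are affected through the entry rules.** The counting rule is common to all three, but for supine pulse, supine blood pressure and ALT/AST the entry limits lie inside the MAV limits, and Protocol 7.0 has eligibility confirmed at both Screening and Check-in. What remains outside the ECG is body temperature, standing readings, a change between Check-in and the Day 1 predose value, and laboratory tests without a numeric entry limit.
- **That active is biased against placebo.** Step 6 shows it is not, in expectation.
- **That a Baseline finding is certain to be counted.** The documents give no within-subject repeatability. A heart rate just under 50 bpm, or an interval on its limit, may not recur.
- **That every overlap matters equally.** PR 220 and QTcF 450 are single boundary values, and 450 to 480 ms requires bundle branch block in a healthy volunteer.

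What does not stand is that the other outputs repair the endpoint. The shift tables use the interpretation category, not the MAV limits. The change summaries describe groups. The QTcF change limits are joined to the absolute limit by an or, so they add cases and remove none. Listings let a reader reconstruct Baseline status by hand, but the reported percentage stays unqualified.

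**Conclusion.** The point holds for the ECG endpoint. As planned, it can report a pre-existing ECG heart rate, QRS, QT or QTcF finding as a postdose event, and nothing in the planned tables separates the two. One subject moves a dose level by 16.7 points and pooled placebo by 10 points. The consequence is a primary safety percentage that is inflated in absolute terms and, through chance imbalance in groups of six, can suggest or hide a dose pattern. It does not invalidate the comparison with placebo.

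The size rests on three assumptions: that the item 21 thresholds act as entry limits, that SAP 7.9 governs the pooling (10 placebo subjects per part for the cohorts now listed, more if cohorts are added), and that some enrolled subjects have Baseline findings that persist. Their frequency cannot be derived from the documents, so no corrected rate can be given.

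**What to change.** Leave the entry criteria, the MAV limits and the planned any-postdose count as they are. In SAP 7.9.4 add, for each ECG parameter and direction (low or high), the number and percentage of subjects with a postdose MAV whose Baseline, as defined in SAP 7.1.3, did not meet that same criterion. A cross-tabulation of postdose MAV by Baseline MAV status would serve equally well.

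Two details need stating:
- The QTcF change-from-Baseline limits have no Baseline status, so meeting one counts as emergent by definition.
- A subject already over a limit who worsens, for example QRS 112 ms rising to 140 ms, will not be emergent under this rule. Such subjects stay in the planned count and the listings, so the worsening is not hidden.

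The same row may be added to the laboratory and vital-sign MAV tables for consistency. The cost is one derived flag and one extra row per table. No new data are needed.

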7.9.5 Safety EEG

For EEG interpretation data, shift tables will be provided for the number and percentage of subjects who change status on the interpretation from Baseline to each scheduled postbaseline measurement.

All safety EEG data will be presented in data listings.

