## 9.1.13 Safety EEG Procedure

EEG data will be collected in a resting state with eyes open and closed, with photic stimulation, and with 3 minutes hyperventilation. EEG time may be adjusted in consultation with the PI and sponsor, and based on emerging PK or other data. When an EEG is scheduled at the same time as blood draws, the blood draws will take priority and the EEG will be obtained within 2 hours before or after the scheduled blood draw and/or vital sign assessment.

EEGs will be evaluated by a qualified individual for clinically significant abnormalities. Findings will be categorized as (1) within normal limits, (2) abnormal but not clinically significant, or (3) clinically significant abnormal. Abnormal EEG findings should be described. If a subject has a tremor during the study, an EEG must be conducted as soon as possible.

Prior to randomization, EEG reports must be reviewed by the investigator. Descriptive text reports will be provided for all screening and postdose EEGs. A subject with an EEG categorized as significantly abnormal during screening will not be eligible for randomization. To aid with EEG interpretation, video recordings and live streams of the volunteers' faces may be done during the EEG, at the investigator's and/or qualified individual's discretion.

A study manual of EEG assessments will be prepared and provided to the site before the start of the study. The EEG study manual will be stored with the study file.

Instructions for collecting, processing, and shipping of samples are provided in the laboratory manual.

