- (l) For subjects who meet all other eligibility criteria (eg, clinical laboratory assessments), EEGs will be performed during Screening, Check-in (Day -1), on Day 1 approximately 1.5 hours postdose, Day 2 at least 23 hours but not more than 25 hours postdose, Days 5 and 7, at ET, or if a subject develops a tremor (resting or otherwise). The investigator must review the Screening EEG results and verify that there are no CS abnormalities for the subject to be eligible for randomization.
- (m) C-SSRS: Columbia-Suicide Severity Rating Scale. The C-SSRS (Baseline/Screening version) will be administered at Screening and Day -1 (Check-in). The 'Since Last Visit' version of the C-SSRS will be administered on Discharge Day 5 and Study Exit Day7, ET.
- (n) CC
- (p) For SRD Cohorts 1 to 5, blood samples (4 mL) for PK analyses will be collected at predose (within 15 minutes prior to dosing) and at 0.25, 0.5, 1, 1.5, 2, 3, 4, 6, 8, 10, 12, 16, 24, 36, 48, 72, 96, 120, and 144 hours postdose.
- (q) PTEs will be collected from signing of informed consent up until dosing on Day 1.
- (r) Any event after dosing on Day 1 will be captured as an AE.

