|---------------------|--------------------------------|--|--|--|--|------------------|
| Screening | Check-in Assessments (a) | TAK-653 Dosing Study Assessments (a) (b) (c) | Safety and PK Assessments (a) (c) | PK Assessments | PK Assessments/ Study Exit (a) | |
| Day -28 to -2 | Day -1 | Day 1 | Days 2-5 | Day 6 (Cohorts 1-5) Days 6-7 (Cohort 6 onward) | Day 7 (Cohorts 1-5) Day 8 (Cohort 6 onward) | Day 14 (±2) |
| | ← | Confinement — | > | | | |

Part 1: SRD Study Schematic

(a) EEG assessments are scheduled on Days -1, 1, 2, and 5, at Study Exit, and at ET.

(b) Study assessments include PK sample collection throughout.

(c) CC

(d) Follow-up will occur by telephone unless abnormal, clinically significant findings are observed upon discharge. In this case or at investigator's discretion, subjects should return to the clinic for re-evaluation.

The planned first dose level to be studied is 0.3 mg for SRD Cohort 1. The actual choice of the dose levels in subsequent Cohorts will occur after the full review of all available blinded safety, tolerability, PK, and PD data in the preceding cohorts. If necessary, the sponsor team (Takeda only) may unblind the data and perform additional analyses for an informed dose-escalation

| TAK-653-1001 | Page 9 of 32 |
|---------------------------------|----------------|
| Statistical Analysis Plan Final | 22 August 2017 |

decision. The next dose level may be higher, lower, or remain the same as the preceding dose level. If the dose is not increased in the next Cohort, staggered dosing is not necessary.

| | TAK-653 Single Dose (b) (c) | | |
|-------------------------------|-----------------------------|---------|-------------------------|
| Cohort (a) | Planned | Actual | No. of Subjects |
| 1 | 0.3 mg | 0.3 mg | 6 TAK-653 2 placebo |
| 2 | X mg | 1.0 mg | 6 TAK-653 2 placebo |
| 3 (food-effect cohort) (d) | X mg | 3.0 mg | 6 TAK-653 2 placebo |
| 4 | X mg | 5.0 mg | 6 TAK-653 2 placebo |
| 5 | X mg | 9.0 mg | 6 TAK-653 2 placebo |
| 6 | X mg | 18.0 mg | 6 TAK-6536 2 placebo |

Part 1: Summary of SRD Dose Cohorts

(a) Sentinel dosing will occur at the start of each Cohort in the SRD. After the investigator and sponsor review the 24-hour safety and tolerability data, the remaining subjects can be dosed in a staggered fashion (no more than 3 subjects at a time). A 24-hour gap will follow each subsequent administration to evaluate safety and tolerability data.

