A single dose of TAK-653 or placebo will be administered on Day 1 followed by approximately 120 hours for safety, tolerability, PK, and PD assessments. Once daily (QD) multiple dosing will begin on Day 6 and continue through Day 18 (13 days). Initiation of the multiple-dose phase on Day 6 may be adjusted based on emerging safety, PK, and/or PD data. Neither sentinels nor staggered dosing are used in the SRD/MRD. Subjects in the SRD/MRD Cohorts will be kept in the study unit for at least 72 hours after the last dose for safety assessments before discharge. The total confinement period planned is 21 days. Cohort 4 as well as any additional cohorts are optional (Note: at the time of this SAP, Cohort 4 has been initiated), to be used if emerging safety and/or PK or PD data warrant further study at a different dose. Follow-up assessments will occur on Day 31 (±2).

Each dose cohort will be examined sequentially to ensure adequate evaluation of all available safety tolerability PK and PD data prior to administering the next dose level

Part 2: SRD/MRD Study Schematic

| Pretreatment Period | | Treatment Period | | | | Follow- up (e) | |
|---------------------|-------------------------------------|---|--|---|---------------------------------|-------------------|----------------|
| Screening | Check-in Baseline Assessments | TAK-653 Single Dose Study Assessments (a) (b) (d) | Safety and PK Assessments (d) | TAK-653 QD dosing Study Assessments (a) (b) (c) (d) | Safety and PK Assessments | Study Exit | |
| Day -28 to -2 | Day -1 | Day 1 | Days 2-5 | Days 6-18 | Days 19-20 | Day 21 | Day 31 (±2) |
| | 4 | | Confin | ement | | • • • • • • • • | |

(a) Study assessments include PK sample collection throughout.

(b) EEG assessments are scheduled on Days 1, 11, 18, and ET.

| (C) | |
|-----|----|
| (d) | CC |

(e) The Follow-up assessments will occur by telephone unless abnormal, clinically significant findings are observed upon discharge. In this case or per investigator's discretion, subjects should return to the clinic for re-evaluation.

| | Planned TAK-653 Dose (a) (b) (c) | | | |
|--------|----------------------------------|--------|-----------|--|
| Cohort | Planned | Actual | Subjects | |
| 1 | X mg | 0.3 mg | 6 TAK-653 | |
| | | | 2 placebo | |
| 2 | X mg | 1.0 mg | 6 TAK-653 | |
| | | | 2 placebo | |
| 3 | X mg | 3.0 mg | 6 TAK-653 | |
| | | | 2 placebo | |
| 4 | X mg | 6.0 mg | 6 TAK-653 | |
| | | | 2 placebo | |
| 5 | X mg | 9.0 mg | 6 TAK-653 | |

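### No planned table delivers the EEG primary endpoint: SAP 7.9.5 offers only shift tables at scheduled visits, and an abnormality seen only on a tremor-triggered EEG enters no EEG summary

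*SAP*

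**What the plan says.** SAP 5.1 lists among the primary endpoints: "Percentage of subjects who experience clinically significant abnormal changes in EEG measurements at least once post-dose". Protocol 5.4.1 has the same endpoint. It is counted per subject, over any time after dosing, and is not limited to scheduled recordings.

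The analysis is in SAP 7.9.5. EEG interpretation is summarised by shift tables "from Baseline to each scheduled postbaseline measurement". The only other output is a listing: "All safety EEG data will be presented in data listings".

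The scheduled times are in the two schematics of SAP 4.4. For Part 1: "EEG assessments are scheduled on Days -1, 1, 2, and 5, at Study Exit, and at ET". For Part 2: "EEG assessments are scheduled on Days 1, 11, 18, and ET".

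Protocol 9.1.13 adds a recording with no fixed time: "If a subject has a tremor during the study, an EEG must be conducted as soon as possible". Footnote (l) of Protocol Appendix A places the same trigger after the fixed days: "at ET, or if a subject develops a tremor (resting or otherwise".

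For laboratory data, SAP 7.9.2 counts subjects with at least one markedly abnormal postdose result and says that all results in the window, "including scheduled and unscheduled measurements, will be included in the MAV summaries". SAP 7.9.3 and 7.9.4 do the same for vital signs and ECG.

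**The concern.** The endpoint asks whether a subject ever had a clinically significant abnormal EEG change after dosing. The planned tables ask what each subject's status was at each scheduled visit. These are different quantities, and the second does not determine the first.

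The mismatch falls on the recordings closest to the trial's main safety question. Convulsions and tremors are named as key risks in Protocol 6.2.4 and are the two adverse events of special interest in Protocol 10.1.5. Under Protocol 6.3.1, one subject with a tremor and seizure-type EEG changes meets a cohort stopping criterion, whereas tremor without such changes needs more than one subject. The EEG that separates these two cases is the one taken because of the tremor. It belongs to no scheduled visit, so it has no place in a table organised by scheduled measurement.

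**Working it through.** The plan gives no event rate, power or precision for this endpoint, and SAP 6.0 says that the sample size was not based on power. There is no planned figure to reproduce. The check compares endpoint with analysis, followed by an illustration of size.

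1. **Endpoints against tables.** Four primary endpoints in SAP 5.1 count subjects with an abnormality at least once after dosing.

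| Endpoint | Per-subject count planned | Unscheduled results |
|---|---|---|
| Laboratory | Yes, SAP 7.9.2 | Included |
| Vital signs | Yes, SAP 7.9.3 | Included |
| ECG | Yes, SAP 7.9.4 | Included |
| EEG | None in SAP 7.9.5 | No rule; shift tables name scheduled measurements only |

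2. **Can the shift tables be added up?** No. If the visit counts of abnormal subjects are a1, ..., ak among n subjects, the number ever abnormal lies between max(a) and min(n, sum of a). Suppose that at one dose level (n = 6) one subject is abnormal on Day 11 and one on Day 18. The number ever abnormal is 1 if they are the same person (1/6 = 16.7%) and 2 if they are not (2/6 = 33.3%). The tables look the same in both cases.

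3. **Does another section fill the gap?** SAP 7.11 moves only the pharmacodynamic EEG analysis outside the SAP. Protocol 13.1.6.4 plans a shift table of subjects who changed status from Baseline and does not limit it to scheduled measurements. SAP 7.9.5 is narrower, and SAP 7.11 does not record this as a change.

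4. **Where would an abnormality seen only on a tremor-triggered EEG appear?** The EEG would be in the listings. The tremor or seizure would be in the TEAE tables of SAP 7.9.1. The EEG result itself may have no adverse event term, because Protocol 10.1.3 tells sites not to record accompanying signs as additional events. It would be in no EEG summary.

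5. **Size, as an illustration.** Assume one active subject whose only clinically significant EEG is tremor-triggered. SAP 4.4 gives 6 active subjects per cohort, and its Part 2 table has 5 cohorts, so 5 × 6 = 30 active subjects. Intervals are exact (Clopper-Pearson) 95%; with no events the upper limit is 1 − 0.025^(1/n).

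| Group | EEG abnormalities found at scheduled measurements only | Any postdose EEG |
|---|---|---|
| One dose level, n = 6 | 0/6 (0 to 45.9%) | 1/6 = 16.7% (0.4 to 64.1%) |
| Pooled TAK-653, Part 2, n = 30 | 0/30 (0 to 11.6%) | 1/30 = 3.3% (0.1 to 17.2%) |

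Part 1 has 6 cohorts in SAP 4.4, or 36 active subjects. SAP 7.9 presents SRD Cohort 3 separately, which leaves 36 − 6 = 30 in the main summary and the same figures as the second row.

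**The case against.** The best defence is that little would be hidden. A tremor-triggered EEG presupposes a tremor, and tremors and convulsions are tabulated as TEAEs. A convulsive seizure is also on the medically significant list in Protocol Table 10.a, and so is a serious event. Every EEG is listed, and with 6 active subjects per dose a reader will see one abnormal entry. Dose decisions rest on cohort review and the stopping criteria, not on an end-of-study table. An abnormality that lasts to the next scheduled EEG enters that shift table. All of this stands, and it limits the consequence. It does not produce the endpoint. A TEAE table counts the tremor, not the EEG result, and so does not separate tremor with seizure-type changes from tremor without them.

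A second defence is that the counts for other measures apply numeric limits, while EEG is a three-category reading. On this view the proper parallel is ECG interpretation, which has the same shift-table sentence. The parallel is fair as far as it goes. But the ECG endpoint is defined on numeric criteria and has its own count, whereas the EEG endpoint is defined on the reading and has none.

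It can also be said that SAP 7.1 and 7.9 promise numbers and percentages for categorical and other safety data in general, and that SAP 7.9.5 has no sentence excluding unscheduled EEGs. That is correct. The gap is an absent table and an absent rule, not an express exclusion. General wording still does not tell a programmer to build the table.

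Four stronger readings are tempting, and the documents do not support them:

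- **That such an event would be counted in no summary at all.** The TEAE tables count the tremor or seizure.
- **That the endpoint would be reported as 0%.** The shift tables do not produce the endpoint, so they cannot produce a false zero for it.
- **That early-termination EEGs are left out.** Both schematics in SAP 4.4 call them scheduled.
- **That a transient event would usually fall between scheduled EEGs.** No probability is given or can be derived. Part 2 has 14 dosing days (Day 1 and Days 6 to 18), Protocol 9.3.4 adds an EEG at Study Exit, and the Part 2 EEG schedule in Appendix C is partly blacked out.

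**Conclusion.** The point holds in this form. SAP 7.9.5 contains no table that yields the EEG primary endpoint of SAP 5.1, and its by-visit shift tables cannot be converted into it. A clinically significant abnormality found only on the mandatory tremor-triggered EEG would be listed, with the related tremor or seizure in the TEAE tables, but would be absent from every EEG summary.

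The difference is one subject in 6, or 16.7 percentage points, at a dose level, and 3.3 points in pooled Part 2. Both figures assume a single such subject, on active drug, whose scheduled EEGs show no clinically significant change. They are not a forecast: Protocol 4.3 reports no CNS-type adverse events in the cohorts completed by Amendment 06. No hypothesis test or sample size depends on this. The correction is still worth making, because it concerns a primary safety endpoint tied to the trial's named key risks.

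**What to change.** Add to SAP 7.9.5 the number and percentage of subjects with at least one postdose clinically significant abnormal EEG change from Baseline. State that all postdose EEGs count: scheduled, early-termination and unscheduled, including tremor-triggered. Present it by pooled placebo, each TAK-653 dose level and pooled TAK-653 within each part, with the food-effect cohort shown as SAP 7.9 sets out. Keep the by-visit shift tables as supportive.

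The cost is one sentence and one table. Protocol 9.1.13 already has each EEG classified into the categories needed, so neither data collection nor trial conduct changes.
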